The study will therefore provide valuable information on the impact of MUP and will form an important component of the planned evaluation portfolio (coordinated by NHS Health Scotland). Effects of the intervention on important population subgroups (including by deprivation, age and sex) will also be reported.

2. Introduction

2.1 Background

It has been suggested that alcohol is the most harmful substance to society once all the health, social and economic costs are accounted for [1]. The level of alcohol-related harm in the UK in general, and Scotland in particular, is high and is a major contributor to socio-economic Inequalities [2, 3]. It is also increasingly acknowledged to be a global problem, with alcohol ranked as the ninth most common cause of death worldwide [4]. The over-consumption of alcohol is associated with a multitude of health problems including an increased risk of liver disease, heart disease, unintended pregnancy, sexually transmitted infections, some cancers and accidental injuries [5-7]. Its impact extends beyond the individual, with adverse effects on families, communities and the wider economy.

A comprehensive evidence review found evidence that consistently confirms a link between alcohol price, consumption and harm, although the strength of the association varies between studies [8]. From a UK perspective, the cost of alcohol has not risen in line with the rise in disposable income and alcohol was 44% more affordable in 2010 than it was in 1980 [9]. The evidence suggests that price mechanisms, such as taxation or MUP, to restrict affordability offer some of the most effective strategies to reduce alcohol-related harm but there is limited published research to date evaluating the particular strategy of minimum unit pricing [6, 8]. Although some forms of minimum pricing have been in place in some provinces in Canada for a number of years, MUP represents a somewhat distinct policy since it sets a minimum price based purely on the alcohol content of a beverage, thereby reducing the likelihood of substitution effects. Econometric modelling suggests that introducing a MUP would have a considerable impact in Scotland and England [10-12].

Minimum unit pricing has widespread support within the Public Health community [5, 13, 14]. The National Institute for Health and Clinical Excellence has published guidelines presenting a clear case for pursuing minimum unit pricing for alcohol, with evidence underpinning the recommendation from a comprehensive systematic review and modelling exercise [15]. NHS Health Scotland has led the Scottish Government's evaluation of Scotland's alcohol strategy through the Monitoring and Evaluating Scotland's Alcohol Strategy (MESAS) programme [16]. MESAS focused on evaluating licensing reforms, delivery of alcohol brief interventions and specialist treatment services. NHS Health Scotland plans to build on MESAS by using routinely collected data to assess changes in price, consumption and alcohol-related harms at a population level that occur as a result of MUP.

The work planned by NHS Health Scotland relies on routinely collected data and hence there are a number of areas of the MUP intervention that they cannot assess, in particular individual level changes in drinking and acute health harms not captured by routine data; and the possible unintended consequences of MUP and the likely differential impact of such consequences on the young and/or disadvantaged populations. Unintended consequences may occur through: increases in the use of illicit or industrial alcohol, use of other substances, and/or reducing the buying of food rather than alcohol to offset increased prices.

This study therefore, aims to build on the planned NHS Health Scotland research programme to assess changes in drinking behaviours and selected acute health harms not captured by routine data. Different mechanisms may cause varied impacts on population sub-groups. As with any pricing policy, MUP is likely to affect drinkers on lower incomes, and those who consume greater quantities, disproportionately. This research will therefore look at potential disproportionate effects by comparing the impact across different socioeconomic groups.

Alcohol-related harm in the UK in general, and Scotland in particular, is high and is a major contributor to health inequalities. MUP has been identified as an important potential public health policy intervention to address the burden of alcohol-related health harms and to reduce health inequalities. The Alcohol (Minimum Pricing) (Scotland) Bill was introduced to the Scottish Parliament on 31st October 2011 and passed in May 2012. Following the passage of the legislation into law, MUP has been subject to substantial delays as a consequence of a series of legal challenges. However, in October 2016 the Scottish Court of Session ruled in favour of the legality of MUP [17], raising expectations that the policy may finally be implemented. However, the Scotch Whisky Association has exhausted the legal options, with a final appeal to the UK Supreme Court having failed in November 2017 [18]. The Scottish Government now plans to implement MUP on 1st May 2018. As a consequence of the implementation of MUP relatively soon, it is important that baseline data be collected as soon as practicably possible.

Scotland will therefore be the first country to introduce MUP nationally. If so there will be a clear difference in policy between Scotland and England. MUP is expected to have significant health impacts, but with uncertainty about size and adverse consequences. These divergent policy options coupled with uncertainty about effect size, and with the interest in MUP elsewhere in the UK and internationally, provide the opportunity to evaluate MUP as a natural experiment [19]. Evidence from Canada is confined to retrospective analysis of routine data on price, consumption and selected harms [20-23]. NHS Health Scotland plan to undertake analysis similar to that in Canada, of routine data to determine the impact of MUP on price, consumption and alcohol-related hospital admissions and deaths in Scotland. This will rely on routinely collected data and hence there are a number of areas of the MUP intervention that it cannot assess, in particular changes in drinking and acute health harms not captured by routine data; and the possible unintended consequences of MUP and the likely differential impact of such consequences on the young and/or disadvantaged populations.

Changes in acute health harms:

Alcohol-related attendances to Emergency Departments (EDs) are strongly associated with both levels of population consumption and population harms ([name], paper in preparation). Alcohol-related attendances to EDs that do not result in admission are not routinely collected and so will not be included in MESAS. There is a need for robust, prospective evaluation evidence to measure the effectiveness of MUP in changing this important health outcome; to determine if and how it alters alcohol use, and to monitor possible differential impacts and potential adverse consequences. Our proposed assessment of changes in alcohol-related attendances at EDs will help establish the effects of MUP on alcohol-related harms. It will also add to the evidence base on the burden alcohol places on EDs. It will make an important contribution to our understanding of the effects of MUP, which routinely collected data may miss as there is potential for secular trends to occur (for example, related to the economic downturn[24] and hospital admissions data will be subject to time lags that may make establishment of causality based purely on routine data more difficult [25]. Furthermore, primary data collection planned in this study makes use of reliable validated tools (the Fast Alcohol Screening Test (FAST) which is a shortened form of the AUDIT questionnaire designed for use in emergency departments) [26]. This tool not only quantifies levels of harmful alcohol use but allows detection of changes in drinking patterns [27]. Such information is currently not adequately collected within routine health surveys, particularly for young people and deprived populations who are most likely to be affected by the intervention [28]. Assessment of drinking patterns is crucial as different patterns of consumption (for example binge drinking compared with chronic levels of use) are associated with different patterns of health and other social harms [6, 29].

Potential unintended consequences:

A number of potential unintended consequences have been identified that might arise from the introduction of MUP:

- 1) Consumers may switch to alternative sources of alcohol not subject to MUP so that the price paid does not increase. Such sources include both legal (internet sales from outwith Scotland, legitimate cross-border purchase for own use [30], and home fermentation) and illegal sources (counterfeit, smuggled or stolen alcohol) [31, 32].
- 2) Increased alcohol-related harm could occur through substitution (e.g. to illicitly produced or industrial alcohol associated with greater toxicity) or changed drinking patterns (e.g. moving from regular drinking to binge drinking).
- 3) Displacement effects with reductions in alcohol-related harms being accompanied by increases in harms related to other substance use could be observed, and
- 4) MUP could unfairly penalise deprived populations less able to absorb the additional financial cost [33] and this may adversely affect access to other essentials such as food.

There is a need for robust, prospective evaluation evidence to measure the effectiveness of MUP in changing alcohol-related emergency department attendances; to determine if and how it alters alcohol use, whether it changes public attitudes and norms and perhaps more importantly to monitor possible differential impacts and potential adverse consequences. To the investigators' knowledge, no other studies are planned to detect these adverse impacts in a robust way. Investigation of these potential impacts is of major public health importance as it may have important impacts on the overall assessment of health benefits compared to harms, as well as the distribution of those harms.

This proposal is informed by the MRC guidance on using natural experiments to evaluate population health interventions [19] and is based on a similar framework to the portfolio of studies investigating the smoking ban in public places in Scotland [34]. Evidence on the impacts, both positive and negative, will be of interest to the public, politicians and the public health community in Scotland, the rest of the UK and internationally.

2.2 Rationale

The legislation introducing MUP includes a so-called 'sunset clause', formally a provision that the measure will expire at the end of six years, unless an order for continuation is made between the fifth and sixth year [35]. A decision on whether implementation should continue is to be based on findings from a comprehensive evaluation, which this work constitutes an important part. The need for an evaluation is also stipulated within the Alcohol (Minimum Pricing) (Scotland) Bill which states that Scottish Ministers must present to the Scottish Parliament a report on the operation and effect of the minimum pricing provisions. This report must include information about how the policy has affected relevant businesses, different population subgroups and health.

The SPHSU has considerable expertise required to carry out this evaluation. In particular, the Unit's Policy programme focuses on methodology to evaluate natural experiments and led the development of the MRC's guidance in this area. Similarly, the Inequalities programme has a long history in evaluating major public health policies (for example, the National Evaluation of Sure Start) and in particular, assessing their impact on health inequalities.

2.3 Aims/Objectives/Research questions

The overarching NIHR grant includes three related studies that together make an important contribution to the overarching evaluation of the impact of MUP in Scotland. The three research

aims and their associated studies are summarised in the Table below. The remainder of this protocol will only focus on the Emergency Department (ED) study, with a separate protocol available for the survey of alcohol-related behaviours (which involves data collection within sexual health clinics).

Research aims (RAs)	Study components
RA1: To determine the impact on alcohol-related harms	Emergency Department study;
and drinking patterns for the overall population and by	Survey of alcohol-related
subgroups of interest (age, sex and deprivation)	behaviours (C1)
RA2: To determine the impact on non-alcohol substance	Survey of alcohol-related
use for the overall population and by subgroups of interest	behaviours(C2); Qualitative focus
(age, sex and deprivation).	group study (C3)
RA3: To describe changes in experiences and norms	Qualitative focus group study (C3)
towards MUP and alcohol use following the introduction of	
MUP by subgroups of interest (age, sex and deprivation).	

The more specific research objectives (ROs) of the ED study are as follows:

- 1. To determine the impact of MUP on alcohol-related ED attendances amongst the general population
- 2. To determine whether the effect of MUP differs across the following population subgroups
 - a. Age group
 - b. Gender
 - c. Area-based deprivation
- 3. To determine whether the effect of MUP varies dependent on the type of alcohol-related harm:
 - a. Acute alcohol-related harms vs chronic alcohol-related harms
 - b. Broad diagnostic groups (on the basis of ICD categories)
- 4. To investigate whether alcohol consumption (on the basis of the FAST score: sensible, hazardous, harmful, possible dependence) has changed amongst people attending EDs over time
- 5. To investigate whether the intervention effect size varies over time

3 Study Design/Methods

3.1 Study Design

This research is a natural experiment study of the impact of introducing MUP in Scotland. The methods involve a repeated cross-sectional audit of all alcohol-related attendances at EDs in two Scottish hospitals and two North England geographical control hospitals at three time points. On each occasion, data collection will involve a face-to-face survey administered by research nurses to ED patients over selected times during a three week time period. All study documents with the exception of the patient information sheet and consent form will be

electronic and held on an iPad. Back up paper copies will be available in case of iPad failure. The study methods and tools are based on previous studies that have been used to quantify the national prevalence of alcohol-related attendances in Emergency Departments in England [36] and by the experience of the Scottish Emergency Department Alcohol Audit, carried out across 15-20 hospitals throughout mainland Scotland between October 2005 and June 2007 [37]. Prior to formal data collection, the processes for collecting data will be piloted – initially within Glasgow only, followed by pilot data collection at all four sites.

The study has been designed to be robust to potential delays in the timing of the intervention. Since the implementation of MUP is not under the control of the investigators, it is possible that there may be delays in the timing of the intervention. Baseline data collection will occur as soon as is practically possible. The 2nd and 3rd waves of data collection will take place six and 12 months post implementation. If implementation of MUP occurs more than 12 months after baseline the 2nd wave will be conducted shortly before implementation to act as a 2nd baseline. The 3rd wave will remain as close to a 12 month follow-up as feasible. If this occurs, it will not be possible to investigate whether the intervention effect varies over time (RO5). In general, investigators will attempt to avoid conducting data collection during months that are expected to be atypical in terms of alcohol consumption (i.e. Dec-Jan and Jun-Aug). Furthermore, we will attempt to collect data for one follow-up wave at the same time of year as the baseline data, to control for seasonal variation in consumption.

Since the design of the study is by necessity non-randomised, there remains potential for confounding. Furthermore, given the need to include high-risk drinkers within the study, previous experience has demonstrated that it is not possible to conduct longitudinal research with satisfactory rates of follow-up. For this reason, repeated cross-sectional samples have been chosen. However, the validity of analysis of repeated cross-sectional samples require high response rates and for participants interviewed to be representative of the population from which they are drawn (i.e. attenders to the ED in this study). It is therefore crucial that considerable effort is made to ensure that all eligible patients attending ED during data collection periods is invited to participate. The absolute number of participants within the study is far less important.

3.3 Participant Selection

The target population for the study is all patients over 16 years age who attend EDs to receive acute treatment for a health condition.

The exclusion criteria for the sample are used to decide whether to approach patients and having approached whether the patient is eligible:

Deemed clinically inappropriate to be approached.

- 'patient too unwell',
- · too distressed,
- grossly intoxicated (alcohol),
- grossly intoxicated (drugs)
- Cognitive impairment
- · Police in attendance,
- Clear language barrier, and no interpreter available
- · Patient already participating,
- routine follow up that has been instigated by ED staff,
- Patient left dept
- Patient admitted,
- staff safety issue,
- End of shift,
- dead on arrival,
- other.

For those who are approached, the inclusion criteria are:

- >=age16
- able to speak English and no interpreter available.
- Is a new ED presentation,
- The patient is conscious
- The patient is physically well enough
- The patient is mentally well enough
- The patient is sober enough (alcohol)
- The patient is sober enough (drugs)
- The patient is still in the department
- The patient is safe for staff to approach

During data collection periods, an ED attendance database will be maintained for all attendances to allow monitoring of patient recruitment. This will help prevent patients being approached on multiple occasions. This attendance database will be destroyed at the end of each recruitment shift. In addition, data on sex, five year age group and diagnoses for all attendees in all the three week waves, with the attendees within the study timeslots flagged, will be requested from hospital records. This is to enable the assessment of the representativeness of our sample and of our estimates of the proportion of alcohol-related attendances.

We intend to obtain a total sample size of at least 2820 participants across all four sites over each three week period of data collection. This equates to 235 participants per week per site of data collection. No target sample size is required for the pilot phases of the study as these phases are intended to help identify potential practical issues involved in conducting the study.

Based on the experience of the 24 hour audit of Emergency Departments in England, we have assumed that we will be able to recruit at least 50% of eligible ED attendees. We anticipate that the four sites will result in 940 recruits per week. Recruiting over three weeks pre- and post-intervention – giving a total sample size of 5640 – would mean that we would be highly powered (>80%) to detect a decrease in the proportion of alcohol-related attendances from 30% to 25% with 95% significance. We have used a base rate of 30% informed by the 24 hour audit of EDs in England and assumed a 5% decrease would be of public health importance and may be expected based on current evidence. For subgroup analyses, we would have good power (>80%) to detect an effect size of 0.23 on the FAST score among those from the most deprived quintile (estimated to be 25% of attendances) and an effect size of 0.27 among those aged 18-24 (estimated to be 15% of attendances. Two separate follow-up times are required to determine if intervention effects vary over time.

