3.8 Data Analysis

Primary outcome

The primary outcome will be changes in absolute numbers of alcohol-related attendances as defined by any one of:

- patient self-reports attendance is alcohol-related
- patient reports alcohol consumption in past 24 hours of ≥8units in men or ≥6 units in women
- patient not approached because too intoxicated with alcohol

Secondary outcomes

Secondary outcomes will be changes in:

- absolute number of alcohol-related attendances by age/sex/deprivation
- problematic alcohol use (as defined by the Fast Alcohol Screening Test (FAST))
- mean FAST score
- prevalence of binge drinking in the past week
- reason for attendance (coded by ICD10)

After the first post-intervention wave, we will test for differences in the outcomes between the intervention and comparison groups using a fixed-effects regression model, with individuals nested within EDs, before and after adjustment for relevant covariates including baseline levels of alcohol-related attendance, demography, triage category etc. We will also attempt to determine the nature of the effect more precisely in terms of whether a dose-response effect according to the time since MUP was implemented (through a test of the significance of an interaction between time and intervention). We will test for interactions of the intervention with defined important covariates (including age, gender, deprivation quintile, disease diagnostic categories) to investigate the possibility of differential intervention effects and will subsequently stratify the analyses if indicated.

4. Research Governance and Regulatory Issues

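### The >80% power stated for a fall from 30% to 25% fits only a two-group comparison; for the same proportion, the controlled Scotland-versus-England change has about 55% power with one post-MUP wave

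*Protocol*

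**What the plan says.** The design in section 3.1 covers "two Scottish hospitals and two North England geographical control hospitals at three time points". Section 1 describes the main study as a comparison of the Scottish with the English hospitals over those time points.

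Section 3.3 sets the recruitment: "We intend to obtain a total sample size of at least 2820 participants across all four sites over each three week period of data collection". It adds: "This equates to 235 participants per week per site of data collection". The power statement takes one wave before and one after, "giving a total sample size of 5640", and concludes that the study "would be highly powered (>80%) to detect a decrease in the proportion of alcohol-related attendances from 30% to 25% with 95% significance". On the starting value it says: "We have used a base rate of 30% informed by the 24 hour audit of EDs in England". The paragraph does not say which two groups are compared. It mentions no change in the control hospitals and no variation between EDs over time.

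For the analysis after the first post-intervention wave, section 3.8 says "we will test for differences in the outcomes between the intervention and comparison groups using a fixed-effects regression model". Individuals are nested within EDs, and the covariates include the baseline level of alcohol-related attendance. The primary outcome there is the change in absolute numbers of alcohol-related attendances, and it counts patients who were not approached because they were too intoxicated.

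**The concern.** The power paragraph describes one proportion falling from 30% to 25% in 5640 people. Half of those people attend hospitals where MUP is not introduced. Once the English change is subtracted, the estimate carries the sampling error of four cells instead of two, roughly doubling the variance of a comparison of 1410 with 1410. A calculation for two groups then overstates the power of the controlled comparison.

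Section 3.3 treats a fall of 5 points as important for public health and plausible. Section 2.2 says that the wider evaluation informs whether MUP continues. If the controlled analysis gives an inconclusive result, readers will judge it partly by the power that the protocol claimed.

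**Working it through.** **Inputs**
- 235 per site per week (section 3.3) × 2 sites × 3 weeks = 1410 per country per wave. Over four sites this is 2820 per wave, and 2 × 2820 = 5640, as stated.
- Proportions 30% and 25% (section 3.3).
- Significance level 5%. The protocol does not state sidedness; two-sided is assumed.
- Change in England: not given. Assumed none (30% to 30%).
- Patients assumed independent.

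**Reproducing the stated figure (two groups)**

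Power = Φ[(0.05 − 1.96 × √(2 × 0.275 × 0.725 / n)) / √((0.21 + 0.1875) / n)]
- n = 1410 per group: (0.05 − 1.96 × 0.01682) / 0.01679 = 1.015, so power is 84.5%. This is Scotland before v after, or Scotland v England after.
- n = 2820 per group: (0.05 − 1.96 × 0.01189) / 0.01187 = 2.25, so power is 98.8%. This is all four sites before v after, and it needs the unexposed English EDs to fall to 25% as well.

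Both satisfy the stated >80%.

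**Controlled contrast, one post-MUP wave**

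(Scotland after − Scotland before) − (England after − England before), four cells of 1410:
- SE = √((3 × 0.21 + 0.1875) / 1410) = √(0.8175 / 1410) = 0.0241
- Power = Φ(0.05 / 0.0241 − 1.96) = Φ(0.116) = 54.6%
- Detectable at 80% power: (1.96 + 0.84) × 0.0241 = 6.7 points

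Checks: 54.7% by simulation (200,000 runs), 56.8% on the logit scale, 66.7% if one-sided. Varying the English rate from 20% to 40% gives 60% to 52%. Power of 80% for 5 points would need 0.8175 × 7.85 / 0.0025, about 2567 per cell, or about 10,270 in all.

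**Controlled contrast, both post-MUP waves**

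After-cells of 2820, before-cells of 1410:
- SE = √((0.21 + 0.21) / 1410 + (0.1875 + 0.21) / 2820) = 0.0209
- Power = Φ(0.05 / 0.0209 − 1.96) = 66.5%
- Detectable at 80% power: 5.9 points

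**ED-by-wave variation (assumed range, not in the protocol)**

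With two EDs per country, a standard deviation s between ED-waves adds 4 × s²/2 = 2s² to the variance. With one post-MUP wave, s = 1 point gives SE = √(0.000580 + 0.0002) = 0.0279 and power 43%. For s = 2 points, SE = √(0.000580 + 0.0008) = 0.0371 and power is 27%.

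**Count scale (illustration, Poisson assumed)**

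Expected counts are 0.30 × 1410 = 423 in three cells and 0.25 × 1410 = 352.5 in the fourth. The log ratio is ln(0.25/0.30) = −0.182, with SE = √(3/423 + 1/352.5) = 0.0996. Power is Φ(0.182/0.0996 − 1.96), about 45%. With both post-MUP waves the same approach gives about 57%. Patients too intoxicated to approach are not in these counts, because the protocol gives no number for them.

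**The case against.** **The contrast behind the stated figure is not named.** A reader might infer that the protocol computed the power of a Scotland-only before/after comparison. The text does not support this as fact: Scotland v England after MUP gives the same 84.5%, and pooling all four sites also exceeds 80%. The subgroup figures in section 3.3 lean towards 1410 per group (0.23 in 25% of attendances gives 86.3%; 0.27 in 15% gives 79.3%). They do not settle it, since 79.3% is not above 80%. This objection stands. It does not rescue the claim, because none of these readings nets off the English change.

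**55% is not the power for the primary outcome.** This also stands. Section 3.8 defines that outcome as absolute numbers and includes patients who were never recruited. The 55% belongs to the proportion in section 3.3.

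**Clustering is not ignored.** Section 3.8 nests individuals within EDs, and ED fixed effects remove stable differences between hospitals. It would be wrong to say that the plan makes no allowance. What remains is variation within an ED from wave to wave. Its size is unknown, so the 43% and 27% above are only illustrations.

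**There are two follow-up waves, 2820 is a minimum, and section 3.1 puts representativeness above numbers.** All true. But section 3.3 bases its claim on one post-MUP wave, and using both gives 67%. Representativeness may justify the chosen sample size, but not a wrong power figure.

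**Conclusion.** The concern holds in this form: the power in section 3.3 is correct for a two-group comparison and wrong for the controlled comparison that sections 1, 3.1 and 3.8 describe. For the proportion, power is about 55% with one post-MUP wave and about 67% with both, against the stated >80%; the detectable differences are about 6.7 and 5.9 points, not 5. These figures assume no change in England, 1410 per country per wave, independent patients and a two-sided 5% test. ED-by-wave variation would lower them.

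Two stronger conclusions are tempting but not supported. One is that the study must recruit more: the error lies in the stated power, and section 3.1 gives reasons for the design that do not rest on numbers. The other is that a null result will be taken as proof of no effect. That is a risk of the wording, not something the protocol says, and section 1 presents the study as one component of a wider evaluation.

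**What to change.** In section 3.3, delete the claim of high power (>80%). In its place, give power and detectable difference for the country-by-period contrast and list the assumptions: English change, cell sizes, independence and sidedness. Either calculate these for the primary outcome as section 3.8 defines it (absolute numbers, including patients too intoxicated to approach), or say explicitly that they apply to the proportion. In the latter case the figures are about 55% and 6.7 points with one post-MUP wave, and about 67% and 5.9 points with both. State that ED-by-wave variation is not included and would reduce power.

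The fix should not make the pooled waves 2 and 3 contrast the primary effect. That would change the estimand and sit badly with three parts of the plan: the test after the first post-intervention wave (section 3.8), the objective on variation over time (RO5, section 2.3), and the contingency that turns wave 2 into a second baseline (section 3.1).

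The cost is a short recalculation, a change of wording and a less favourable stated power. No site, wave or participant is added.

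### The >80% power stated in protocol section 3.3 for FAST effects of 0.23 and 0.27 in two subgroups does not hold for the planned comparison of changes between groups, which needs about 0.30 and 0.39

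*Protocol*

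**What the plan says.** Section 3.3 of the protocol sets a "total sample size of at least 2820 participants across all four sites over each three week period of data collection", which it equates to 235 per site per week. The power statement rests on "Recruiting over three weeks pre- and post-intervention", 5640 people in all. For the primary outcome it takes a fall from 30% to 25% "with 95% significance". The subgroup claim opens with "we would have good power (>80" per cent). Its first part, on deprivation, is that this power is available "to detect an effect size of 0.23 on the FAST score among those from the most deprived quintile (estimated to be 25% of attendances"). Its second part, on the younger patients, puts the detectable size at "an effect size of 0.27 among those aged 18-24 (estimated to be 15% of attendances"). The contrast, the unit of the effect size and the sidedness of the test are not given.

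Section 3.1 describes two Scottish hospitals and two control hospitals in North England, surveyed at three time points. Section 3.8 lists the secondary outcomes as changes, mean FAST score among them. It tests the outcomes between the intervention and comparison groups in a regression that allows for ED, with and without adjustment that includes baseline levels of alcohol-related attendance. It continues: "We will test for interactions of the intervention with defined important covariates", naming age, gender and deprivation quintile, with stratified analyses to follow if indicated. Research objective 2 in section 2.3 is "To determine whether the effect of MUP differs across the following population subgroups".

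**The concern.** A change compared between two countries uses four cell means, whereas a simple comparison uses two. With equal cells and independent samples the variance doubles, and the smallest detectable effect rises by a factor of √2, about 1.41. If 0.23 and 0.27 belong to a two-cell contrast, they describe a more sensitive study than the one section 3.8 analyses.

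This matters because sections 2.1 and 2.2 give differential effects on young and deprived groups as one of the reasons for the study, and say that the statutory report must cover population subgroups. A reader told that power is good may take a null subgroup result as evidence that there is no effect there.

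**Working it through.** **Inputs**
- Per country and wave: 235 × 3 weeks × 2 sites = 1410 (sections 3.1 and 3.3). Check: 4 × 1410 = 5640.
- Most deprived quintile, 25%: n = 0.25 × 1410 = 352.5 per country-wave cell. Ages 18-24, 15%: n = 0.15 × 1410 = 211.5.
- Samples are repeated cross-sections (section 3.1), so no within-person correlation reduces the variance.
- Assumptions not in the protocol: effect size in SD units, two-sided 5%, equal sites, no clustering by ED, no gain from covariates.

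**Formulas.** With SD = 1, the minimum detectable effect (MDE) at 80% power is (1.960 + 0.842) × √V = 2.802 × √V. Power at effect d is Φ(d/√V − 1.960).

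**Step 1: look for the plan's own figures.** Two groups of n, V = 2/n:
- 25%: √(2/352.5) = 0.0753; MDE 0.211; power at 0.23 is Φ(1.09) = 86%.
- 15%: √(2/211.5) = 0.0972; MDE 0.272; power at 0.27 is Φ(0.82) = 79%.

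This comes close to the stated sizes. It fits one country before v after, and equally Scotland v England at one wave. The primary-outcome claim behaves in the same way: 30% v 25% with 1410 per group has 84.5% power, against 54.6% for a controlled difference of 5 points. A before/after contrast over all four sites would have 99% and 98% power for the two FAST sizes, but it does not separate the countries.

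**Step 2: the contrast in section 3.8.** The difference in change between countries has V = 4/n with one post wave. With both post waves pooled, V = 2 × (1/n + 1/(2n)) = 3/n.

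| Within-subgroup controlled effect | √V | MDE | Power at stated size |
|---|---|---|---|
| 25%, one post wave | 0.1065 | 0.298 | 58% at 0.23 |
| 15%, one post wave | 0.1375 | 0.385 | 50% at 0.27 |
| 25%, post waves pooled | 0.0923 | 0.258 | 70% at 0.23 |
| 15%, post waves pooled | 0.1191 | 0.334 | 62% at 0.27 |

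**Step 3: sensitivity.** Covariates would need to explain about 41% (25% subgroup) and 51% (15% subgroup) of FAST variance for the one-post-wave contrast to reach 80% power at the stated sizes, or about 21% and 35% with the post waves pooled. A one-sided 5% test (multiplier 1.645 + 0.842 = 2.486) with pooled post waves gives MDEs of 0.229 and 0.296, so it would just meet the first figure and still miss the second.

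**Step 4: supplementary, FAST interaction of subgroup v all others.** With m = 1410 − n (1057.5 and 1198.5), V = 4/n + 4/m with one post wave:
- 25%: 2.802 × √(4/352.5 + 4/1057.5) = 0.345 (0.3446).
- 15%: 2.802 × √(4/211.5 + 4/1198.5) = 0.418.

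With pooled post waves, V = 3/n + 3/m gives 0.298 and 0.362.

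**The case against.** The strongest reply is that section 3.3 never says which contrast it has in mind. It promises only more than 80% power, and for a two-group contrast that is true of 0.23 (86%) and within rounding of 0.27 (79%). Research objective 4 also speaks of FAST among ED attenders over time, which a simple comparison could address. This stands as a reason not to call the arithmetic wrong. It does not rescue the claim for the planned analysis, because section 3.8 treats mean FAST score as a change and tests it between groups.

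Several stronger readings are tempting, and the protocol does not support them:
- **That the English controls were ignored.** The match with one country before v after is an inference. Scotland v England at one wave has the same numbers and does use the controls.
- **That 0.23 should be 0.21.** The 0.23 is not presented as the minimum detectable effect, and a claim of more than 80% is met by 86%.
- **That the two figures cannot share a method.** Their ratio is 0.27/0.23 = 1.17, against √(25/15) = 1.29. That comparison is informative only if both are exact MDEs at the same power under simple sampling, which is not stated.
- **That interaction power is misstated.** No interaction power is claimed; the claim concerns effects within subgroups. The interaction figures also depend on a subgroup-v-rest contrast that the protocol does not specify. A five-level or trend test over deprivation quintiles would give others. They concern FAST only, while objective 2 also covers alcohol-related attendances.
- **That every planned subgroup test has under 60% power.** With the post waves pooled, the within-subgroup tests reach 70% and 62%.

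**Conclusion.** The concern holds in this form: at the stated sizes, the controlled comparison in section 3.8 does not have the power that section 3.3 claims. With one post wave, the basis of the protocol's own 5640, power is 58% and 50%, and the detectable effects are about 0.30 and 0.39 SD. With both post waves pooled, power is 70% and 62%, and the detectable effects are 0.26 and 0.33 SD.

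These figures rest on the assumptions listed in the working. Change over time that differs between EDs would raise the detectable effects, and covariate adjustment would lower them. The point affects the power statement for a secondary outcome in subgroups. It does not show that the study design or the analysis model is wrong.

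**What to change.** In section 3.3:
1. Name the contrast to which the subgroup figures refer.
2. Replace 0.23 and 0.27 by the controlled minimum detectable effects: about 0.30 and 0.39 with one post wave, and 0.26 and 0.33 with both pooled. State the assumptions (SD units, two-sided 5%, equal sites, no clustering by ED, no covariate gain).
3. Remove the claim of good power at 0.23 and 0.27.
4. Because section 3.8 tests subgroup differences by interaction, add a labelled supplementary line: for FAST, subgroup v rest, the detectable interaction is about 0.34 and 0.42 SD with one post wave, or 0.30 and 0.36 pooled. Say that a null interaction is therefore not evidence that there is no differential effect.

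This is a change of protocol wording. It needs no change to recruitment, data collection or the analysis model. The cost is that the stated figures become less favourable.
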